8.3.4 Dosage/Dosage Regimen

19 participants @ < 40 kg, given 1 mg at each of 2 attacks
19 @ < 40 kg given 4 mg at each of 2 attacks
19 @ ≥40 kg given 2 mg at each of 2 attacks
19 @ ≥40 kg given 8 mg at each of 2 attacks

8.3.5 Dispensing

The investigators will give the participants the study bottles at their clinic visit, or the study bottles will be sent to them.

8.3.6 Administration Instructions

The study team will instruct the participant and a parent as to how and when to take the study chocolates.

8.4 Supply of Study Drug at the Site

Good Day Chocolate will send the chocolate to the site and the site will repackage the chocolate pieces into study pill dispensing bottles.

8.4.1 Storage

The study bottles will be stored in a locked cabinet at room temperature.

8.5 Study Drug Accountability

An accurate and current accounting of the dispensing and return of study drug for each subject will be maintained on an ongoing basis by a member of the study site staff. The number of study drug dispensed and returned by the subject will be recorded on the Investigational Drug Accountability Record. The principal investigator will verify these documents throughout the course of the study.

8.6 Measures of Treatment Compliance

Participants will be asked how many chocolate pieces they took for each attack and they will be asked how many of the Extra Pieces were either dropped/thrown away and how many were kept for a future or other attack.

9 STUDY PROCEDURES AND GUIDELINES

Prior to conducting any study-related activities, written informed consent and the Health Insurance Portability and Accountability Act (HIPAA) authorization must be signed and dated

by the subject's parent or legal guardian. Age appropriate assent will be obtained from the child or adolescent prior to conducting any study-related activities.

9.1 Clinical Assessments

9.1.1 Concomitant Medications

Pertinent concomitant medication and concurrent therapies will be documented at Baseline/Screening. Dose, route, unit frequency of administration, and indication for administration and dates of medication will be captured.

9.1.2 Demographics

Demographic information (date of birth, sex, race) will be recorded at Screening.

9.1.3 Medical History

Relevant medical history will be recorded at Screening.

9.1.4 Physical Examination

Participants will have had physical examinations performed as part of their clinical care at the UCSF Pediatric Headache program. No additional physical examinations will be needed for study purposes.

9.1.5 Vital Signs

See 9.1.4

9.1.6 Adverse Events

Participants and parents will be able to report adverse events at any time during the study. Duration (start and stop dates and times), severity/grade, outcome, treatment and relation to study drug will be recorded on the case report form (CRF).

9.1.7 Pregnancy Determination

During enrollment, female subjects who are of childbearing age will be asked if they could be pregnant.

10 EVALUATIONS BY VISIT

10.1 Visit 1

Baseline data will be collected by either an investigator and/or the study coordinator either in-person in the clinic, via a recommendation by their doctor or another member of the study team, or via phone for those enrolling remotely. All participants will have already been verified to meet ICHD criteria for episodic migraine. Headache duration, history, preventive medication use pattern, acute medication use pattern, aura status, family history, associated symptoms, comorbidities, pregnancy status and other variables will be assessed via questioning either in the clinic, chart review or via phone/text.

Participants will be instructed to treat two migraine attacks with their assigned melatonin dose. For those randomized to either 1mg or 2mg, they will receive 4 extra pieces in case they drop or lose any, or would like to use a different headache to track in the event that they take the melatonin and then something comes up where they are unable to track that headache for 24 hours.

For those randomized to 4mg or 8mg, they will receive 8 extra pieces. Participants are instructed that they are able to keep any unused pieces for a future attack but will be asked to return the empty bottles. Families will be asked to write down on the front cover of the headache diary how many of the extra pieces were either kept for later attacks, or were lost/dropped/thrown away. Alternatively, the study team will ask the families and record this for them. The diary asks how many chocolate pieces were taken for each attack.

Migraine attacks should be separated by at least 24 hours' headache freedom in between.

Participants will be provided with the Good Day sleep chocolate product and told their randomly assigned dose (either 1mg or 4mg for under 40kg, and either 2mg or 8mg for greater than or equal to 40kg). They will be given three bottles:

- Bottle 1 is labeled **Attack #1** and will have their exact dose (as described above)
- Bottle 2 is labeled **Attack #2** will have their exact dose (as described above)
- Bottle 3 is labeled **Extra** and will have either 4 or 8 pieces so they can have enough extra pieces if they drop or lose some of the pieces from bottle 1 or 2, as well as so they can use some if they want to treat another attack (they have been instructed to only use the dose they are assigned to)

Chocolate melatonin supplies will be given to the parents for all young children who, in the opinion of the investigator, may need additional supervision. If a child were to eat all of the chocolate melatonin pieces at once, this would still be considered a safe amount, as neonates have been safely given 10mg/kg IV melatonin³.

They will also be given a paper headache diary (either in person or shipped). They will be instructed to treat as early as possible in an attack, i.e. ideally while the pain is still mild, however they will still be permitted to treat even if the pain has reached the moderate or severe levels. Participants will be asked to treat attacks that occur at home (or attacks that are not yet treated when they reach home), or that occur at another location where they can stay for at least 8 hours if needed, so as to ensure driving after dosing will not be necessary (for older teens), and that headache diaries will be available, and participants can sleep after dosing if desired.

Participants will record baseline pain intensity (and other migraine symptom intensity) at time zero, i.e. right before they dose the melatonin. They will be asked not to take other acute medications for two hours, and to record pain intensity (and other symptom intensity) at 30, 60, 90 min and the two-hour time marks. If they fall asleep, parents/caretakers will be instructed **not** to wake them for data collection, as sleep may be a mechanism by which melatonin helps acute

migraine. They will resume data collection as soon as they first awaken. They will be asked to collect data also at 4 hours and 24 hrs, and to record any acute medication used between 2-24 hours. They will also be asked to record their impressions about the treatment's efficacy, side effects, and whether or not they slept after dosing and if so for how long.

Study staff will contact participants until they complete the study to remind them about when to treat an acute attack and to answer any questions. Participants may be sent 'retention' packages (small office supplies, pens, or other small items) to remind them about the study. At the completion of the study, participants will be asked to mail back the headache diary in a pre-paid FedEx envelope. A \$5 gift card will be given to participants once they mail back the diary.

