8.2 Blinding

This is an open label study and there is no blinding

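### Families know their dose before choosing, within limits, which two attacks to treat, so the time-zero VAS behind the primary change score could differ by arm through choice

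*Combined protocol and SAP*

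**What the plan says.** Section 8.2 (Blinding) states: "This is an open label study and there is no blinding". In section 10.1 (Visit 1), families are handed the product and "told their randomly assigned dose" before any attack is treated. The instruction on which attacks to use is: "Participants will be instructed to treat two migraine attacks with their assigned melatonin dose".

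Three provisions in section 10.1 limit the choice:

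- **Separation:** "Migraine attacks should be separated by at least 24 hours' headache freedom in between".
- **Location:** attacks should be treated at home, or somewhere the child can remain for 8 hours if needed.
- **Timing:** "They will be instructed to treat as early as possible in an attack, i.e. ideally while the pain is still mild". The same sentence goes on to say that "they will still be permitted to treat even if the pain has reached the moderate or severe levels".

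Section 8.3.3 also foresees that a family may decide to use the spare pieces on a different attack. The synopsis sets no time limit on participation other than the time taken to treat two attacks.

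Baseline pain is recorded in each treated attack immediately before dosing (section 10.1). The primary GEE (section 14.2) compares change from that value and mentions only control for repeated measures. Section 14.1 lists sex, age and weight for summary by dose level; time-zero VAS is not listed. Section 14 says that an SAP is still to be written.

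**The concern.** In most trials the baseline of a change score is fixed before allocation, so randomisation balances it. Here it is the pain score at the start of an attack that the family chose to treat, at a moment the family chose, knowing the dose. Change from baseline depends on baseline: an attack dosed at 2 cm cannot improve by the 3 cm the trial is sized to detect. Section 1.2 itself says that treating while pain is mild predicts efficacy for other acute treatments, so the protocol regards pain at dosing as prognostic.

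If the arms came to treat different kinds of attack, the high-minus-low difference would mix dose with attack choice. The secondary endpoint of reaching mild or no pain could move the other way, because an attack dosed at mild pain already meets it. The trial's purpose is to select a dose for a placebo-controlled study, and that calls for comparable treated attacks. Nothing planned would show whether they were comparable.

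This is separate from unblinded pain scoring. It concerns which attacks and which starting scores enter the analysis, and it can be addressed without blinding.

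**Working it through.** **Plan's own figures (synopsis, Statistics).** The inputs are a difference of 3 cm and an SD of 3. Alpha and power are not stated; two-sided 5% and 80% are assumed.

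- One attack: n = 2 × (1.96 + 0.84)² × 3²/3² = 15.7, so 16 per arm. This matches.
- Two attacks: 12/16 = 0.75 = (1 + ρ)/2, which implies a within-person correlation ρ = 0.5. The variance of a participant's mean change is then 9 × 0.75 = 6.75.
- Enrolment: 12/(1 − 0.35) = 18.5, so 19 per arm; 4 × 19 = 76. This matches.

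The sample-size chain is not in dispute. It supplies the standard errors below.

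**Standard error of the dose difference**, SE = √(2 × 6.75/n):

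- Both weight strata pooled, n = 2 × 12 = 24 per arm: SE = 0.75 cm.
- One weight stratum, n = 12 per arm: SE = 1.06 cm.

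**Bias from a baseline shift.** Let D be the between-arm difference in mean time-zero VAS caused by choice, and c the movement in change score per cm of baseline. Then bias = c × D. The documents give neither quantity. The assumed ranges are D = 0.5 to 1.0 cm and c = 0.3 to 0.7.

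- Smallest: 0.3 × 0.5 = 0.15 cm, which is 0.15/3 = 5% of the target.
- Largest: 0.7 × 1.0 = 0.70 cm, which is 0.70/3 = 23% of the target.

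**Two-sided rejection rate when the doses do not differ**, by normal approximation: Φ(bias/SE − 1.96) + Φ(−bias/SE − 1.96).

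| Bias (cm) | 24 per arm | 12 per arm |
|---|---|---|
| 0.15 | 5.5% | 5.2% |
| 0.35 | 7.5% | 6.3% |
| 0.50 | 10.2% | 7.6% |
| 0.70 | 15.4% | 10.1% |

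**If the bias ran against a true 3 cm effect**, power in one stratum of 12 per arm, Φ((3 − bias)/SE − 1.96), would fall from 80.7% to 76.6% (bias 0.15) or 58.3% (bias 0.70). With D = 0 there is no bias from this source.

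**The case against.** The strongest reply is that the choice is far from free. The separation, location and treat-early instructions apply to both arms, and staff stay in contact until completion to remind families when to treat. A reader might infer that families may use any two attacks they like; the text does not support that. The treat-early advice bears directly on time-zero VAS. What stands against the reply is that these provisions narrow the set of attacks without saying which of the remaining ones to use, and dosing at any pain level is permitted.

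A reader might also infer a direction, for example that high-dose families save their pieces for bad attacks. The documents do not support this. Bottles 1 and 2 each hold one full dose in every arm, and the spares cover at least one more full dose in every arm (8 pieces at 8 mg is one; the other arms have two or four). Scarcity gives no reason to hold back, and the opposite behaviour is as plausible.

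Nor does it follow that randomisation has failed. High versus low remains a valid comparison of open-label assignment, including how families respond to knowing the dose. What weakens is its reading as the effect of dose on similar attacks.

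Two further points are fair. The magnitude rests wholly on assumed inputs, and its low end is negligible. The diary and the verbal instructions promised in section 8.3.6 are not in the documents and may say more, so the gap is established only for the protocol text.

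**Conclusion.** The point holds as a possible bias, worth a cheap correction. The documents establish a known dose, incompletely specified attack choice, a baseline measured after allocation is known, and a primary model that names no baseline covariate. They do not establish that the arms will choose differently, or in which direction.

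The bias of 0.15-0.7 cm and the error rates of about 5.5-15% (24 per arm) or 5.2-10% (12 per arm) are illustrative. They depend on the assumed shift and slope, on ρ = 0.5 as implied by the plan's reduction from 16 to 12, and on a two-sided 5% test that the plan does not state. Since the pilot selects a dose on effectiveness, then tolerability, then lowest dose, the error rate is only a rough gauge of the effect on that decision.

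The case for acting now is that attacks passed over and never recorded cannot be reliably recovered by an SAP written later.

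**What to change.** - **Section 10.1 and the diary:** ask families to use Bottles 1 and 2 for the first two attacks that meet the conditions section 10.1 already sets, and to note any such attack left untreated, with the reason. This is one diary line, or one question at the existing reminder contacts.
- **Reporting:** tabulate untreated eligible attacks and time-zero VAS by dose arm.
- **Analysis:** pre-specify, as a sensitivity analysis, the primary GEE with time-zero VAS added as a covariate. This is needed because the attack rule alone does not address pain level at dosing. It is a partial remedy: that score is itself measured after allocation is known, and unrecorded features of the attacks may still differ.

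The cost is one instruction, one diary line, one descriptive table and one extra model. Diary burden rises slightly, and the log is self-reported by families who know their dose. No change to dose, eligibility or rescue rules is proposed.

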DURATION OF SUBJECT PARTICIPATION AND DURATION OF STUDY	Participation duration depends on how long it takes to treat two migraine headache attacks. In total, it will take approximately 2-3 hours to complete the study. Enrollment will take place over 24 months.
CONCOMITANT MEDICATIONS	
Allowed: All
 
Prohibited: N/A
 
Acute migraine medications such as ibuprofen (Motrin), acetaminophen (Tylenol), naproxen (Aleve) or a triptan (for example, sumatriptan) may be taken during the study, but we will ask participants to try to wait 2 hours after they take the study treatment, in order to see if the study treatment is effective.

EFFICACY EVALUATIONS	VAS pain scores between baseline and 2-hr time point
PRIMARY ENDPOINT	To determine a change in mean VAS score between baseline and 2-hr time point in low-dose vs. high-dose group.
SECONDARY ENDPOINTS	
 • To determine a change in mean VAS score between baseline and 2-hr time point in low-dose vs. high-dose group in the < 40 kg and the ≥40 kg subgroups. (We will also do sensitivity analyses of completers who were awake for the 2-hr time point). • To determine the tolerability/side effects of high-dose vs. low-dose in the group over all, and in weight-basedstrata. • To determine the proportion of participants who get to mild/no pain by 2 hrs (overall and by weight group), and who remain at mild/no pain from 2-24 hours • To determine the proportion of participants who get to mild/no of each of: pain, photophobia, phonophobia, nausea, vomiting at 30, 60, 90, and 120 minutes and 24 hours; both overall and in weight based strata.

	
 • To determine the proportion of parents/participants who found the treatment useful, and who preferred it over other treatments they'd tried. • Using logistic regression, we will examine for possible predictors of treatment efficacy (sex, age, nap, nap duration, etc). • To determine the proportion of participants who needed rescue medication between 2-24 hrs, both overall and by weight- based strata.
OTHER EVALUATIONS	Headache Diary
SAFETY EVALUATIONS	Incidence of adverse events.
PLANNED INTERIM ANALYSES	Serious adverse events will be monitored by the PI and the UCSF IRB on an ongoing basis throughout the study.

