3.2 Secondary Objectives

- To determine a change in mean VAS score between baseline and 2-hr time point in low-dose vs. high-dose group in the < 40 kg and the ≥ 40 kg subgroups. (We will also do sensitivity analyses of completers who were awake for the 2-hr time point).

- To determine the tolerability/side effects of high-dose vs. low-dose in the group over all, and in weight-based strata.
- To determine the proportion of participants who get to mild/no pain by 2 hrs (overall and by weight group), and who remain at mild/no pain from 2-24hours
- To determine the proportion of participants who get to mild/no of each of: pain, photophobia, phonophobia, nausea, vomiting at 30, 60, 90, and 120 minutes and 24 hours; both overall and in weight based strata.
- To determine the proportion of parents/participants who found the treatment useful, and who preferred it over other treatments they'd tried.
- Using logistic regression, we will examine for possible predictors of treatment efficacy (sex, age, nap, nap duration, etc).
- To determine the proportion of participants who needed rescue medication between 2-24 hrs, both overall and by weight- based strata.

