7 CONCURRENT MEDICATIONS

There are no concurrent medication restrictions except as above in the exclusion criteria..

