7.1 Allowed Medications and Treatments

Standard therapy for migraine is allowed except for treatments noted in the exclusion criteria described above. Acute migraine medications such as ibuprofen (Motrin), acetaminophen (Tylenol), naproxen (Aleve) or a triptan (for example, sumatriptan) may be taken during the

study, but we will ask participants to try to wait 2 hours after they take the study treatment, in order to see if the study treatment is effective.

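### Other acute medication is discouraged but not barred before 2 hours, yet its described recording and the rescue endpoint both start at 2 hours, so an early-medicated attack can count as a response without rescue

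*Combined protocol and SAP*

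**What the plan says.** **Waiting period.** The synopsis (Concomitant Medications) allows acute migraine drugs during the study, "but we will ask participants to try to wait 2 hours after they take the study treatment", and the same entry reads "Prohibited: N/A". Section 7.1 repeats the request. Section 7 adds: "There are no concurrent medication restrictions except as above in the exclusion criteria". Section 10.1 is firmer, "They will be asked not to take other acute medications for two hours", but this is still a request, and no consequence is attached to breaking it.

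**Recording.** After the scheduled symptom scores, section 10.1 asks families for data at 4 and 24 hours "and to record any acute medication used between 2-24 hours". The only other medication record described is the one taken at baseline or screening (section 9.1.1).

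**Endpoints.** Section 3.2, repeated in the synopsis and section 5.2, includes "To determine the proportion of participants who needed rescue medication between 2-24 hrs". It also includes "To determine the proportion of participants who get to mild/no pain by 2 hrs (overall and by weight group", with a sustained version to 24 hours. Neither states what happens to an attack in which another drug was taken before 2 hours.

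**Analysis.** Section 14.2 gives the GEE for the 2-hour VAS change. Section 14.3 gives no scoring rules for the efficacy secondaries. Section 14 says a SAP will be written before the final analysis.

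**The concern.** Early use is foreseen, since families are only asked to try to wait, but the described recording and the rescue definition begin where the waiting period ends. An attack medicated at 60 minutes therefore falls outside the rescue endpoint unless something more is taken after 2 hours. If the other drug works by 2 hours, the same attack also counts as mild/no pain. A child who turned to another drug can then appear as a melatonin response that needed no rescue.

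The trial is meant to choose the dose for a later placebo-controlled study. It is open label (section 8.2) and families are told their dose (section 10.1), so early use could differ between doses. A later SAP can add a scoring rule, but it can apply that rule only if early medication and its time were asked for while the diary was being kept. That makes the recording instruction the part that cannot be repaired afterwards.

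**Working it through.** The plan has no figure for early medication, so there is none to reproduce on this point. The check has a textual part and an illustration with assumed rates.

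**1. Following one attack through the text.** Melatonin at time zero, ibuprofen at 60 minutes, mild pain at 2 hours, nothing further to 24 hours.
- Is the ibuprofen prohibited? No (synopsis; section 7).
- Is it a named violation? Not clearly. The medication item in section 13 concerns prohibited drugs, and the synopsis lists none. The list is open-ended, and the general definition mentions primary endpoint criteria, so early use might be logged, but the protocol does not say so.
- Is it described as recorded? Not in section 10.1, whose window starts at 2 hours, and not in section 9.1.1, which is a baseline record.
- Does it count as rescue? No; it lies before the window.
- Does the attack count as mild/no pain at 2 hours? Yes; nothing excludes it.

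**2. Denominators.** From the synopsis, 12 with data per group, inflated for 15% drop-out plus 20% asleep, gives 12 / 0.65 = 18.5, so 19, which is the plan's figure. Two weight strata give 38 enrolled per dose.
- 2-hour pain: 12 × 2 strata × 2 attacks = 48 attacks per dose.
- Rescue: children asleep at 2 hours can still report rescue, so only drop-out applies: 38 × 0.85 × 2 = 64.6, about 65 attacks per dose.

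**3. Rescue.** Let e be the share of attacks medicated before 2 hours, s the share of those needing nothing later, and q the rescue rate in the other attacks.
- Over 0-24 hours: e + (1 − e)q
- Over 2-24 hours: e(1 − s) + (1 − e)q
- Difference: e × s, whatever q is.

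**4. Mild/no pain at 2 hours.** Let p be the response in attacks not medicated early and r the share of early-medicated attacks at mild/no pain.
- As observed: (1 − e)p + e × r
- Early-medicated counted as non-response: (1 − e)p
- Difference: e × r.

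With s and r each between 0.5 and 1 (assumed):

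| e (assumed) | Early-medicated attacks per dose, of 65 (rescue) | Of 48 (2-hour pain) | Shift in either endpoint |
|---|---|---|---|
| 5% | about 3 | about 2 | 2.5-5 points |
| 10% | about 6 | about 5 | 5-10 points |
| 20% | about 13 | about 10 | 10-20 points |

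These are per attack. The endpoints are proportions of participants, and the text does not say how two attacks combine into one participant result, so no conversion is attempted.

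**5. Between doses.** Assume p = 30% (low) and 50% (high), and r = 60%.
- Early use 10% in both: as observed 51 − 33 = 18 points; as non-response 45 − 27 = 18 points.
- Early use 20% low, 10% high: 51 − 36 = 15 against 45 − 24 = 21 points.
- Early use 10% low, 20% high: 52 − 33 = 19 against 40 − 27 = 13 points.

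The as-observed difference can equal, fall below or exceed the other, depending on rates that the documents do not give.

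**The case against.** - **The diary may already ask.** The form is not in the documents. A reader might infer that early medication goes uncollected. The text supports only that it is not described as recorded. If the form does ask, the stated rescue window would still leave early use out.
- **The window is coherent.** Families are asked to wait 2 hours, so starting rescue when it becomes acceptable makes sense. That is a fair reason to report a 2-24 hour figure. It does not justify having no figure that counts earlier use.
- **The SAP is still to come, and staff stay in contact with families.** Both are possible routes to a rule and to the information. Neither is a defined procedure, and a rule cannot be applied to data that were not requested.
- **Early medication is not always failure.** It may reflect habit or caution. Section 10.1 encourages dosing while pain is mild, so some attacks are at mild pain from time zero. This stands: non-response is one choice of estimand, which is why the as-observed proportion belongs beside it. Calling these attacks the earliest treatment failures would go beyond the documents.
- **The upper rates are generous.** Eligible families are dissatisfied with earlier treatment or prefer a supplement (section 6.2). They may medicate early less often, or gain less from it. This also stands.
- **The primary endpoint.** A reader might infer that the VAS comparison is invalid or underpowered. Analysing the 2-hour VAS as observed is legitimate. If early use differed by 10 points between doses and the other drug gave 2-4 cm extra relief, the dose difference would move by 0.10 × 2 to 0.10 × 4 = 0.2-0.4 cm, in either direction. With 24 per dose, SD 3, an assumed two-sided 5% level and no gain from the second attack, power against 3 cm is 92%. An adverse shift lowers it to 84-89%.

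**Conclusion.** The point holds for the secondary responder and rescue endpoints. As the protocol is written, an attack medicated before 2 hours can be scored as a 2-hour response and, if nothing is taken later, as free of rescue. At an assumed 10% early use, each of the two proportions shifts by 5-10 points per attack in the favourable direction, given that half to all of those attacks need nothing later (rescue) or reach mild/no pain (response). The shift scales in proportion to the rate.

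Neither that rate nor those shares come from the documents, and the direction of any bias in the dose comparison is unknown and may be nil. The conclusion does not extend to saying that early medication is uncollected or that the primary analysis is wrong. It is a cheap improvement, and the recording part has to be made while diaries are still being filled in.

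**What to change.** 1. In section 10.1, ask families to record the name and time of any acute medication from time zero to 24 hours. If the diary already asks this, only the protocol text needs aligning.
2. Define the rescue endpoint as any use over 0-24 hours, in the synopsis and sections 3.2 and 5.2, and report the 2-24 hour figure as well.
3. State that attacks medicated before 2 hours count as non-responders for mild/no pain at 2 hours, and give the as-observed proportion beside it.
4. Optionally, add to the SAP a sensitivity analysis of the 2-hour VAS that uses the last score before early medication, next to the as-observed GEE.

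When families may take other medication does not change. The cost is one diary line and a few sentences of text, with no new visits or participants. The reported response and rescue rates would look slightly less favourable.
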